Additionally, 20 percent of iSS patients were reported to have cognitive impairment by Kumar et al yet literature reports of cognitive assessment in iSS are few (56). The cognitive dysfunction may be specific to iSS or due to progressive hearing impairment or a combination of both, and further studies are required establish this. Similarly to cognitive function, olfaction has been reported to affect patients with iSS in 17 percent of patients, yet is rarely reported in the literature (8). We therefore will assess the olfactory function and will use (University of Pennsylvania) Smell Identification Test (SIT).

We further hypothesise that there is a genetic predisposition to the development of iSS which may contribute to the degree of associated symptoms. We will collect the saliva samples from the iSS participants (self-collected) to biobank the DNA for genetic analysis during this study or for use in other or future studies.

As part of this study we will collect self-report measures, such as Modified Amsterdam Inventory for Auditory Disability and Handicap (mAIDAH), Speech, Spatial and Qualities of Hearing Scale (SSQ) questionnaire and Tinnitus Functional Index (TFI) adjunct the auditory tests, and Dizziness Handicap Inventory (DHI) and Situational Vertigo Questionnaire (SVQ) alongside the vestibular tests. We hypothesise that these will reflect symptom load and may reflect functional deficits (as

identified on auditory, vestibular and cognitive tests), and we will correlate these with disease severity and the degree of functional impairment.

Because iSS is characterised by auditory and vestibular dysfunction which are reported to be disabling and debilitating it is also important to assess this over time. We hypothesise that the use of interval hearing and balance (vestibular) questionnaires in iSS participants may reflect changes in these functions, which may also be reflective in the quality-of-life questionnaires in these participants, and thus these can be used as a functional outcome measure to monitor disease progression and in the future research and clinical settings – to monitor response to treatment. We hypothesise that these can be used as an adjunct measure of degree of dysfunction and iSS progression than the currently available techniques, including imaging (57).

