13. *Quality-of-life questionnaires* (which can be distributed to the participant ahead of the appointment and collected during their visit, after having given formal consent to participate in the study, as a time saving measure). The quality of life will be assessed using three validated quality-of-life questionnaires:

- *Health Utilities Index-3 (HUI3)* (5mins)
- *EuroQoL Questionnaire (EQ-5D-5L)* (5mins)
- *Evaluation of the Impact of Hearing Loss in Adults (ERSA)*

A follow-up clinical appointment will be also arranged for the siderosis patients (irrespective of their participation in the study). During their follow-up clinical visit, the siderosis patients will undergo the following clinical assessments, as part of their clinical care:

1. *Vestibular evoked myogenic potentials (VEMP)*: calibrated auditory stimuli via ear inserts repetitively presented and neck/eye myogenic (muscle) responses are recorded (20mins)

2. The siderosis patients who have previously consented to participate in the study will then be seen by the research student and the *questionnaires* previously distributed to the study participants will be collected (5mins)

Appropriate break times will be given to the participants during their research study visit. It is anticipated that the total time to complete the assessments will be approximately two to three hours for each visit.

Where the research tests have been completed by the audiologist/clinician/nurse, the research student shall not repeat those during the respective visit but will instead include the results of the tests already performed. Where the clinical tests have not been carried out by the clinical staff (audiologist/clinician/nurse), the research student will carry these out as part of the clinical care pathway and will include the results obtained from the clinical assessments.

Cognitive function will be assessed by means of neuro-psychological testing in line with the clinical care pathway and will be arranged by the clinical team. Imaging will be arranged by the clinical team in line with the clinical care pathway for siderosis patients. With the prior consent obtained from the participants, the results of the clinical assessments (including cognitive and imaging tests) will be obtained and anonymised at source.

Age-related hearing loss group and control group participants' visits and investigations:

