#### Follow-up Investigations:

As a follow-up measure, all study participants will undertake a repeat set of self-report questionnaires after 12 months of their initial completion of the questionnaires (as what would have been completed by the participants at the beginning of the study). These will be sent out to the participants with pre-stamped self-addressed envelopes and will be returned to the research facility by post, or distributed and collected electronically.

The assessments of the siderosis group participants will take place at University College London Hospitals (NHS Foundation Trust). The assessments of the participants from the ARHL group and control group will take place at University College Hospitals (NHS Foundation Trust) London and/or the UCL Ear Institute, depending on the availability of the testing facilities.

The data will be collected and analysed using a dedicated statistical software programme (package) to determine disease-specific pattern and test deficits in iSS and to compare those to the ARHL and the control groups and to the normative data (vestibular function only).

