The research student and the participant (siderosis group participants only) will discuss the research visit and the tests that will take place then and whether the participant is willing to continue their participation in the research project. The research student will then arrange a suitable date/time for the research visit. The clinical follow-up visit will be scheduled by the clinical team and the interval will be decided as clinically necessary.

As a follow-up measure for the research study, all participants will be asked to complete a repeat (identical) set of questionnaires at a 12-month time interval after completing their first set. The identical set of questionnaires will be distributed to the participants by post with a pre-paid self-addressed envelope, or by email and will be returned by post or electronically.

The recruitment will take place over a 24-month period, the assessments and data collection will take place over a 36-month period. The last participant's follow-up appointment is anticipated to be no later than August 2021. The end of the study is defined when the last set of questionnaires is sent-out as a 12-month follow-up measure, whichever one of these events is last. The overall

study duration will be from August 2019 to (end of) July 2022 and will include the time required for data analysis and writing up of the results. Subsequent formal final study report will be put together for the Research Ethics Committee and the sponsor.

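### The plan cannot show that the hearing and balance questionnaires track siderosis progression, because everything scheduled at 12 months is self-report

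*Combined protocol and SAP*

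**What the plan says.** The hypothesis is in section 2 (Rationale) and concerns the siderosis group. Repeated hearing and balance questionnaires, it says, "may reflect changes in these functions, which may also be reflective in the quality-of-life questionnaires in these participants". From this it draws the conclusion that "thus these can be used as a functional outcome measure to monitor disease progression". Response to treatment is named as a later use, and the next sentence presents the questionnaires as an adjunct to existing techniques, including imaging. The paragraph before it says of the self-report measures that "we will correlate these with disease severity and the degree of functional impairment".

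For follow-up, section 5.2 (Follow-up Investigations) states that "all study participants will undertake a repeat set of self-report questionnaires after 12 months of their initial completion of the questionnaires". The Study/Participant Timeline repeats this: "all participants will be asked to complete a repeat (identical) set of questionnaires at a 12-month time interval". Return is by post or electronically.

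In Appendix 2 (Schedule of Procedures), the 12-month column has entries only for the hearing questionnaires and the quality-of-life questionnaires, in all groups. The rows for hearing tests, balance tests (including gait and ataxia scales) and balance questionnaires are empty there. Section 5.2 (Investigations) leaves imaging and cognitive testing to clinical care, although their results may be used. Section 5.5 specifies no analysis of change.

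**The concern.** To show that a questionnaire monitors progression, its change has to be set against something that moves with the disease and is not reported by the same respondent. The plan schedules nothing of that kind at 12 months. What it does collect is two families of self-report, completed by the same person in the same set. Mood, response style and general health can move both together in someone whose siderosis is unchanged. One of the three quality-of-life instruments, ERSA, measures the impact of hearing loss, so it also overlaps with the hearing questionnaires in content.

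The problem does not depend on anyone being treated or fitted with a hearing aid during follow-up. At stake is a recommendation that later studies use these questionnaires to follow progression and treatment response, resting on evidence that cannot separate progression from shared self-report.

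**Working it through.** **1. What can be compared with what.** The Rationale's argument has three links.

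- *Questionnaire change reflects change in hearing and balance function.* This needs function measured again. In Appendix 2 every function test falls under time-points 1 to 3 and none under 12 months. The one test placed at time-point 3 (VEMP) has no earlier measurement. The planned correlation with severity and functional impairment can therefore use only the initial tests. It is cross-sectional and does not set change against change.
- *The change may also show in quality of life.* This can be tested, because both sets are repeated. It is self-report against self-report.
- *The questionnaires can therefore monitor progression.* This needs a measure of progression. None is defined, and no repeat scan is scheduled.

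**2. How readily the testable link is met with no progression.** The protocol has no figure to reproduce: section 7.2.1 says that power and sample size could not be reliably calculated, and no significance level or correlation is given. Inputs:

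- n = 20 to 30 in the siderosis group (Study Summary);
- two-sided 5% level (assumed);
- correlation r between two change scores from shared self-report alone, 0.3 to 0.5 (assumed).

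Fisher z approximation for one pair: P(significant) = Φ(atanh(r)·√(n−3) − 1.96) + Φ(−atanh(r)·√(n−3) − 1.96).

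- r = 0.3, n = 20: 0.3095 × 4.123 = 1.276, giving 0.248.
- r = 0.3, n = 30: 0.3095 × 5.196 = 1.608, giving 0.363.
- r = 0.5, n = 20: 0.5493 × 4.123 = 2.265, giving 0.620.
- r = 0.5, n = 30: 0.5493 × 5.196 = 2.854, giving 0.814.

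At r = 0.4 the results are 0.416 and 0.595.

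Simulation (10,000 studies per case) gave each change score as √r × a common respondent factor + √(1−r) × independent noise, with no disease signal:

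| r | n = 20 | n = 30 |
|---|---|---|
| 0.3 | 0.25 | 0.37-0.38 |
| 0.5 | 0.64 | 0.82-0.83 |

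A separate check with 20,000 runs gave 0.25 and 0.37 at r = 0.3, and 0.64 and 0.83 at r = 0.5. Those are the figures used here. If only 15 sets came back at 12 months, Fisher z gives 0.189 (r = 0.3) and 0.477 (r = 0.5).

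**3. The same check with an independent anchor.** When questionnaire change was correlated with an objective change unrelated to the respondent factor, 0.046 to 0.053 of simulated studies were significant. That is the nominal 5%, whatever the size of the shared factor.

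**4. Precision of a group comparison.** For a difference in mean change between two groups of n, in SD units and without covariates or loss, the 95% half-width is about 1.96 × √(2/n): 1.96 × 0.316 = 0.62 SD at n = 20, and 1.96 × 0.258 = 0.51 SD at n = 30.

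**The case against.** The Rationale states a hypothesis in tentative terms, with no threshold or test. Its first link is to function, not to quality of life, and it presents the questionnaires only as an adjunct. The self-report measures are also to be correlated with severity and functional impairment. Section 5.2 (Comparison) already plans between-group comparison of the questionnaires, and all groups repeat the hearing and quality-of-life sets. Progression monitoring by questionnaire is not among the outcome questions in section 4.2. All of this stands, and it limits how much weight the point carries. It does not supply a second measurement of function or a measure of progression.

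A reader might infer that the plan contains a rule accepting the questionnaires if any questionnaire-to-quality-of-life pair is significant, and so that a positive answer is nearly certain. The documents do not support that. No any-pair criterion appears anywhere. Such a count would also mix in multiplicity: with no shared correlation, and pairs treated as independent, 15 pairs give 1 − 0.95^15 = 54%. Fifteen pairs (5 × 3) further require the balance questionnaires at 12 months, which Appendix 2 does not show. As printed there are 9 (3 × 3).

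The remedy has limits too. Mood or general health could worsen more in siderosis than in the other groups. Hearing in the ARHL group may itself decline, and controls may be as young as 18. The ARHL and control groups complete no balance questionnaires. The consent described in section 5.2 refers to tests already done, so it may not reach tests performed after enrolment.

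**Conclusion.** The concern holds as a mismatch between a stated conclusion and the data scheduled to support it. Following the plan as written would leave a progression-monitoring claim resting on change in self-report alone. The structural point needs no assumption: it follows from section 2, section 5.2 and Appendix 2.

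The size is illustrative. With no progression, one pair of change scores is significant in about 25-37% of studies at r = 0.3 and 64-83% at r = 0.5 (n = 20 to 30), against about 5% with an independent anchor. This rests on the assumed correlations and the assumed two-sided 5% level.

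It would go too far to say that the plan validates the questionnaires against quality of life alone. The link to function is stated, and it can be examined cross-sectionally. What cannot be examined is whether change in the questionnaires follows change in function or disease.

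**What to change.** 1. Analyse 12-month change in the hearing and quality-of-life questionnaires with a group term (iSS against ARHL, and iSS against control), adjusted for age. Do not attribute change to iSS unless it differs from the groups without siderosis. Treat a difference as necessary but not sufficient for a progression claim.
2. Where the clinical notes hold a repeat audiogram or MRI, and consent covers tests done after enrolment, relate questionnaire change to that anchor and report how many participants have it. The balance questionnaires have no comparison group and depend on this step.
3. Without an anchor, conclude only that self-reported change in hearing or balance is associated with self-reported quality of life, and drop the progression-monitoring claim.
4. Reconcile section 5.2, which requires the identical questionnaire set at 12 months, with Appendix 2, which has no 12-month entry for the balance questionnaires. On the schedule as printed, their change would not be collected.

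The cost is analysis wording and a few model terms, with no new visit or test. Consent wording may need attention if it does not extend to later tests. The downside is a more modest claim and a group comparison of low precision.

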### 3. THEORETICAL FRAMEWORK

Because our knowledge of the impact of iSS on hearing and balance is limited and due to progressive and significant morbidity associated with this condition, there is a clear need to improve our understanding of audiovestibular dysfunction and determine its disease-specific pattern. Early recognition of iSS in the clinical setting will enable prompt efforts to halt disease progression by means of initiation of treatment and rehabilitative measures and as a consequence, likely reduction in the associated morbidity.

Extensive battery of hearing tests, including self-report questionnaires, undertaken by the participants will identify test-specific deficits and will reflect which of the tests or their combination best characterise auditory dysfunction in iSS, how these deficits compare to the auditory characteristics in the ARHL group, and which tests most accurately identify hearing dysfunction in both groups. The use of self-report questionnaires in combination with the psychophysical tests will further characterise the auditory and vestibular dysfunction and are thus likely to better reflect functional deficits specific to iSS and ARHL than by means of objective tests alone.

This analysis will achieve a dual goal: firstly, we will be able to determine the disease-specific pattern of hearing loss in iSS and how it compares to age-related hearing loss; and secondly, we will be able to determine which tests or their combination best reflect auditory dysfunction in patients with hearing impairment and are thus likely to be used as markers of function and outcome measures in assessment of sensorineural hearing loss. By employing an extended battery of audiological tests and their combination, we will also attempt to stratify patients with hearing problems based on the likely site of pathology of the auditory pathway and identify those with peripheral deficits from patients with central deficits.

A better understanding of the mechanisms responsible for the patients' audiovestibular symptoms and better localisation of the likely site of pathology within the auditory pathway could have a significant impact on the clinical practice for patients with iSS and for patients with age-related hearing impairment. This study will provide information on the value of audiological and vestibular assessments in iSS and which of those can be applied in the future clinical and research settings as a measure of disease progression and the response to treatment.

## 4. RESEARCH QUESTIONS/AIMS

### Aims

The aims of this study are:

1. To systematically review the literature on audiovestibular function in iSS, including most up-to-date available treatment options;
2. To comprehensively assess the profile of audiological and vestibular dysfunction and its impact on quality of life in iSS in comparison to that of age-related hearing loss (ARHL) and the control groups;
3. To correlate the pattern of hearing loss and vestibular dysfunction in iSS with the imaging findings;

### 4.1 Objectives

1. To determine the audiological and vestibular deficits in patients with iSS and compare these to ARHL and control groups, and to normative data (vestibular function, siderosis group);
2. To correlate the functional deficits and the likely affected structures of auditory and vestibular pathways with brain imaging findings (siderosis group);
3. To determine what combination of tests (including questionnaires) best characterise, quantify and differentiate the auditory dysfunction in the two groups and which tests can be used as optimal outcome measures for diagnosis, monitoring of hearing dysfunction and for hearing rehabilitation;
4. To assess the impact of iSS on quality of life and other functions (olfactory and cognitive) by administering quality of life questionnaires and the Smell Identification Test (SIT) as part of this study. Neuropsychological assessment will be performed as part of clinical care pathway;

## 4.2 Outcome questions

Primary outcome question: What are the salient and disease-specific features of auditory and vestibular dysfunction and what is the impact of iSS on olfactory and cognitive functions and on the quality of life?

Secondary outcome question: How do the imaging findings correlate with the results of audiological, cognitive and vestibular assessments and severity of symptoms?

Tertiary outcome question: Which audiological tests are able to better predict auditory impairment in iSS group compared to the ARHL and the control groups?

Quaternary outcome question: Can a combination of auditory testing approaches be used as a valid functional tool for hearing assessment and site of lesion testing in patients with auditory dysfunction based on the findings of the cohorts included in this study?

## 5. STUDY DESIGN, METHODS of DATA COLLECTION AND DATA ANALYSIS

### 5.1 Study design

This will be an observational study in which three cohorts of participants (two with a known condition, third as a control cohort) will be recruited (58). The auditory function in patients with infratentorial superficial siderosis (iSS) will be compared to the age-related hearing loss (ARHL) group and to the control group with no previous history of hearing loss.

The study protocol has been designed by the Chief Investigator, the study co-investigators/academic supervisors and the research student (study co-ordinator). The STROBE guidelines and checklist for reporting observational studies have been consulted when developing the study protocol (59). Prior to undertaking the study, the protocol has been reviewed by the academic sponsor and is in line with the site-specific regulations.

### 5.2 Data collection methods

All study participants who meet the criteria and have given formal informed consent to take part in this study will undergo the investigations as set out in this study protocol. All research investigations as set out in this protocol will be performed by the research student and/or a designated (and appropriately trained) research nurse and/or designated (and appropriately trained) research audiologist. Because these investigations are used in the clinical practice in the NHS, these may be performed as part of the routine clinical care pathway and in such instances the research student will only complete the investigations which have not been performed during the clinical assessment.

The research student (who is clinically trained) will have the skill, capacity and indemnity to carry out the study assessments. The Chief Investigator will ensure that the research student will have received appropriate training where necessary to carry out the study assessments.

Each participant will be asked permission to notify his or her primary health care team/GP of the involvement in the study. Each participant will be asked if they would like to be made aware of any significant clinical findings identified in the course of the study and whether they would like their primary health care team/General Practitioner to be notified of the findings so that the referral to appropriate services can be made. The participant's decision will be documented in the participants' medical notes (where applicable) and study file during the initial consultation and ahead of any testing taking place. Should the participant not wish to be made aware of any

significant findings during the study, the research student will enquire and ask permission to notify his/hers next of kin and/or the primary care team/GP. Neither the siderosis group participants who consent to saliva sampling and DNA testing nor their primary care teams/GP will be notified of the genetic testing results during the study and as part of other/future studies.

Participants' consent will be sought to access their clinical notes including other tests carried out to date in order to collect the data from their clinical notes in anonymised format and to avoid repeating the tests already performed in the clinical setting.

